1.0 OBJECTIVES

- 1.1 Primary Objective(s)
 - a. To compare event-free survival (EFS) in participants with high-risk resectable melanoma randomized to neoadjuvant pembrolizumab (MK-3475) with participants randomized to adjuvant pembrolizumab (MK-3475).
- 1.2 Secondary Objective(s)
 - a. To assess the frequency and severity of toxicities on each of the arms.
 - b. To compare between arms overall survival (OS), disease control at 24 weeks, locoregional control in the surgical site(s), and total number of pembrolizumab (MK-3475) doses received.
 - c. On the neoadjuvant arm, to estimate the pathologic response rate, the RECIST 1.1 response rate (confirmed and unconfirmed CR and PR), and the iRECIST response rate (confirmed and unconfirmed CR and PR), before surgical resection; to compare definitions of pathologic partial response; and to evaluate the association between pathologic response and EFS and OS.
 - d. To describe the proportion of participants on each arm who received the surgery planned at randomization.
- 1.3 Additional Objective(s)
 - a. To bank tumor tissue and whole blood in anticipation of future correlative studies in this participant population. Such proposed analysis includes deep immune profiling, with evaluation of CD3, CD8, PD-L1, CD20, whole exome sequencing studies, and RNA analysis.

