6.0 STRATIFICATION FACTORS

Participants will be randomized between the Adjuvant arm and the Neoadjuvant arm in a 1:1 fashion, using dynamic balancing. Stratification will be based on:

1. Baseline LDH: Low/Normal (\leq institutional upper limit of normal) versus High ($>$ institutional upper limit of normal) and
2. Stage of disease at randomization: IIIB* versus IIIC* versus IIID*/IV

*Note: **Based on clinical staging as outlined in [Section 4.0](#)**. Participants who have only clinically occult lymph nodes, i.e. N1a-N3a, are not eligible.

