11.2 Analysis plan and sample size justification for primary objective

Based on EFS trends in this participant population, we will use exponential-mixture cure models to describe EFS patterns in the arms. Based on Weber 2017, we assume that on the adjuvant pembrolizumab (MK-3475) arm (null hypothesis) 60% participants will be long-term survivors (or cured or not observed to have an event during the finite follow-up of the trial) and that median EFS for participants who are not long-term survivors will be 2 years. We power this study to detect an alternative EFS in the neoadjuvant arm with 70% of participants being long-term survivors and median EFS among those who are not long-term survivors of 2.5 years. We note that these survival patterns do not follow a proportional hazards assumption and that average hazard ratios from Cox models are expected to become more null with additional follow-up.

We assume 1:1 randomization, accrual over 2 years, and up to 10 years of follow-up after randomization. Under these assumptions the average hazard ratio under the alternative is 0.64. Under the alternative, with a sample size of 500 eligible participants (250/arm), 100% of expected events is 104 events across both arms. At 50% of expected events (51 events, expected approximately when accrual completes), we will perform a futility test testing the alternative hazard ratio from a Cox regression model at the one-sided 2.5% level. No formal interim test of efficacy will be performed. Under the null hypothesis the probability of stopping early for futility is 45% and under the alternative is 2%. The final analysis will consist of a log-rank test of the null hypothesis at the two-sided 15% level (expected 1.5 years after accrual completes). The power of this design is 81%.

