11.3 Sample size re-design

Because accrual to the study has been slower than anticipated, it is expected that 100% of events may be reached before accrual to the study completes, and so the total sample size of the study will be adjusted as follows.

To account for the slower than anticipated accrual rate, a total of 336 eligible, randomized patients will be accrued. If up to 1.5% of patients are not eligible, up to 342 patients will be registered. With the same assumptions for EFS as in the original design, this design should have the same power as the original design using the same alpha. We expect to reach full events within 6 months of completing accrual.

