11.4 Secondary endpoints and analyses

OS, local/regional control, and disease control will be estimated using the Kaplan-Meier method and compared between arms using log-rank tests and Cox regression models. Fisher's exact test will be used to compare the number of pembrolizumab (MK-3475) doses received by participants on each treatment arm. Pathologic response, RECIST 1.1

response rates, iRECIST response rates will be tabulated for the neoadjuvant arm and exact 95% confidence intervals will be constructed. For each arm, 250 participants will be sufficient to estimate toxicity to within $\pm 6\%$. Any toxicity occurring with at least 1% probability is likely to be seen at least once (99% probability).

Primary analyses will all be intent-to-treat. We will perform additional analyses per protocol, to understand how variation in treatment in the neoadjuvant arm can impact the analyses.

CLOSED EFFECTIVE 05/05/2022

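### Section 11.4 overstates the chance of seeing a 1% toxicity in an arm (99% printed, 92% at 250 per arm), and its toxicity figures were not updated after the cut to 168 per arm (82% and ±7.6%)

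*Combined protocol and SAP*

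**What the plan says.** Secondary objective 1.2a is set per arm: "To assess the frequency and severity of toxicities on each of the arms". Section 11.4 supports it with two consecutive statements. The first is "For each arm, 250 participants will be sufficient to estimate toxicity to within" ±6%. The second is "Any toxicity occurring with at least 1% probability is likely to be seen at least once (99% probability".

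The 250 comes from the original design in Section 11.2, "with a sample size of 500 eligible participants (250/arm"). Section 11.3, which is current text, replaces that size because accrual was slow: "a total of 336 eligible, randomized patients will be accrued", and allowing for ineligible patients "up to 342 patients will be registered". Allocation is equal (Section 6.0: "Participants will be randomized between the Adjuvant arm and the Neoadjuvant arm in a 1:1 fashion"). No section restates the toxicity figures for the smaller trial.

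**The concern.** There are two separate faults. The 99% does not follow from the only sample size and unit in the paragraph, which are 250 and a single arm. And both toxicity figures still describe a trial that Section 11.3 has replaced. That section says power and alpha for event-free survival are kept, which is possible because that test is driven by the number of events. Precision for toxicity depends on the number of participants, which has fallen by about a third (250 to 168 per arm).

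What is at stake is how an absence of events is read. The risk table in Section 3.1 has a column of rare but serious reactions below 3%, including myocarditis, Guillain-Barré syndrome, type 1 diabetes and Stevens-Johnson syndrome. A reader who accepts the printed 99% would take zero cases in an arm as near-proof that the rate is below 1%. The trial cannot give that assurance.

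**Working it through.** **Inputs**

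- Participants per arm behind the toxicity statement: 250 (Sections 11.2 and 11.4).
- Current size: 336 eligible, up to 342 registered (Section 11.3). At 1:1 (Section 6.0) that is 336/2 = 168 or 342/2 = 171 per arm. The per-arm numbers are derived, not printed.
- True toxicity rate 1%; stated chance of at least one case 99%; stated precision ±6% (Section 11.4).
- Confidence level: not stated for toxicity; 95% is assumed.

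**Formulas**

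- Chance of at least one case among n participants at rate p: 1 − (1 − p)^n.
- Worst-case 95% half-width, at a rate of 50%: 1.96 × √(0.25/n).

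**Reproducing the plan's figures at 250 per arm**

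- Half-width: 1.96 × √(0.25/250) = 6.2%. The printed ±6% reproduces after rounding.
- Chance of at least one case: 1 − 0.99^250 = 91.9%. The printed 99% does not reproduce. The chance of missing the toxicity is 8.1%, against the 1% implied.
- Participants needed for 99% at a 1% rate: ln(0.01)/ln(0.99) = 458.2, so 459.
- Both original arms pooled: 1 − 0.99^500 = 99.3%. This matches the printed figure and is its likely origin.

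**At the current size**

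| Participants | Chance of at least one case at 1% | Worst-case 95% half-width |
|---|---|---|
| 250 (original arm) | 91.9% | ±6.2% |
| 168 (current arm, eligible) | 81.5% | ±7.6% |
| 171 (current arm, registered) | 82.1% | ±7.5% |
| 336 (current, both arms) | 96.6% | ±5.3% |
| 342 (registered, both arms) | 96.8% | ±5.3% |

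**What 168 per arm can support**

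- Lowest rate seen at least once with 99% probability: 1 − 0.01^(1/168) = 2.7%. At 250 per arm it was 1 − 0.01^(1/250) = 1.8%.
- Zero cases in 168 gives a one-sided 95% upper limit of 1 − 0.05^(1/168) = 1.8%, so it does not exclude a rate above 1%.
- An exact (Clopper-Pearson) interval at a rate of 50% has a half-width of 7.8%, so the normal approximation is adequate here.

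**The case against.** The best defence is that the second sentence names no denominator. Both arms receive the same drug, with 18 planned doses (Section 7.2), so pooling them to ask whether an event is seen at all is reasonable, and at 500 it gives 99.3%. This probably explains where the number came from, but it does not rescue the text. The preceding sentence is explicitly per arm, the objective is per arm, and nothing says the arms are combined. Nor does pooling fit the current trial, where it gives 96.6%. On that reading the error is 2.4 points rather than 17.5.

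Second, ±7.6% is the worst case. At a rate of 20% the half-width with 168 is 1.96 × √(0.2 × 0.8/168) = 6.05%, so ±6% still holds for rates up to about 20%. In the Section 3.1 risk table only fatigue is listed above 20%. This stands: for most single toxicities the printed precision remains adequate. It does not cover commoner events or composite rates.

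Third, no test, stopping rule or decision uses either figure, and safety monitoring runs separately under Section 11.5. That also stands, and it limits the consequence to how the safety results are interpreted.

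Fourth, 168 assumes that every eligible participant is evaluable for drug toxicity. Some adjuvant-arm participants will never start pembrolizumab: Section 5.3 bars those with gross residual disease, and Section 10.10 provides for those who do not register for adjuvant therapy. This makes the position worse. As an assumption for illustration only, if 10% did not start, about 151 would remain, giving 1 − 0.99^151 = 78% and ±8.0%.

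**Conclusion.** The concern holds. Read per arm, as its context requires, the 99% was wrong at the original size by about 7 points. It is now wrong by 17.5 points: the chance of missing a 1% toxicity in an arm is 18.5%, not 1%. The ±6% was correct at 250 per arm and is now out of date; its worst-case counterpart is ±7.6%. The failure to update does not depend on the reading, since pooling the current arms does not reach 99% either.

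These figures assume 168 evaluable participants per arm and a 95% confidence level. The effect is confined to the precision statement for a secondary safety objective. The event-free survival test, its alpha and power, and the monitoring thresholds in Section 11.5 are not touched.

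**What to change.** Replace the two sentences in Section 11.4 with wording along these lines: *With 168 participants per arm, toxicity rates will be estimated to within ±8% (95% confidence interval, worst case at a rate of 50%). A toxicity with a true rate of 1% will be seen at least once in an arm with probability 82%; one with a true rate of 2.7% will be seen with probability 99%.*

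Add that the figures assume all eligible participants in an arm are evaluable for toxicity, or recompute them for the number who receive at least one dose. If a pooled figure is also wanted, label it as such: 96.6% for a 1% toxicity at 336.

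The cost is two sentences and less favourable numbers. No new data and no change to the design or to patient management are needed.

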11.5 Data and Safety Monitoring

A Data and Safety Monitoring Committee will oversee the conduct of the study. The Committee consists of four members from outside of the SWOG, 3 SWOG members, 3 non-voting representatives from the National Cancer Institute (NCI), and the Group Statistician (non-voting). The members of this Committee will receive confidential reports every 6 months from the SWOG Statistical Center and will meet at the Group's bi-annual meetings as necessary. The Committee will be responsible for decisions regarding possible termination and/or early reporting of the study.

In addition to the above DSMC review, toxicity and accrual monitoring are done routinely by the Study Chair, study Statistician, and the Disease Committee Chair. Endpoint monitoring is done by the study Statistician and Study Chair. Accrual reports are generated weekly, and formal toxicity reports are generated every 6 months. In addition, the Statistical Center, Adverse Event Coordinator at the Operations Office, SAE Physician Reviewer, and Study Chair monitor toxicities on an ongoing basis.

After 20, 40, and 60 eligible participants are randomized to the neoadjuvant arm, the following proportions will be tabulated and provided to the DSMC: 1) proportion of participants who develop a higher disease stage (i.e., are upstaged) between randomization and surgery, 2) proportion of participants who become unresectable prior to surgery, and 3) proportion of participants who become ineligible for surgery due to toxicity. At each analysis, we will evaluate whether any of the proportions crosses one of the following thresholds: 1) proportion of participants who develop a higher disease stage (i.e., are upstaged) between randomization and surgery is greater than 25%, 2) proportion of participants who become unresectable prior to surgery is greater than 16%, or 3) proportion of participants who become ineligible for surgery due to toxicity is greater than 5%. If any proportion crosses the corresponding threshold, accrual to the study will be suspended while the study team reviews and evaluates the data from the neoadjuvant arm. Accrual will only re-open after the DSMC reviews the study team evaluation and approves any protocol modifications if proposed.

12.0 DISCIPLINE REVIEW

12.1 Surgical Review and Quality Assurance

All surgeries performed as part of this study will undergo a pathologic response assessment. Refer to [Section 15](#) for specimen submission and labeling instructions. The goal of this review is to verify that the resection was done according to the criteria specified in the protocol ([Section 18.1](#)). The central surgery review will evaluate whether the planned surgical intervention does not change in response to systemic therapy or randomization. This minimizes variables influencing relapse or disease progression by avoiding incomplete or lesser surgery in participants receiving upfront systemic treatment (Neoadjuvant Arm).

Surgical management should follow principles outlined in [Section 18.1](#).

The surgical note originating before study entry describing the planned surgical intervention and the operative report performed on study as part of **S1801** should be submitted to **S1801** Surgical Chair for review. The surgical quality monitoring will be completed by the Surgical Study Chair ([name]). Surgical data including operative notes and pathology reports will be reviewed. Any deviations in surgical quality that are identified will be addressed by the study chairs, Drs. [name] and [name].

13.0 REGISTRATION GUIDELINES

13.1 Registration Timing

Participants must be registered prior to initiation of treatment (no more than 14 calendar days prior to planned start of treatment).

13.2 Investigator/Site Registration

Prior to the recruitment of a participant for this study, investigators must be registered members of a Cooperative Group. Each investigator must have an NCI investigator number and must maintain an “active” investigator registration status through the annual submission of a complete investigator registration packet to CTEP.

13.3 CTEP Registration Procedures

Food and Drug Administration (FDA) regulations and National Cancer Institute (NCI) policy require all individuals contributing to NCI-sponsored trials to register and to renew their registration annually. To register, all individuals must obtain a Cancer Therapy Evaluation Program (CTEP) Identity and Access Management (IAM) account at <https://ctepcore.nci.nih.gov/iam>. In addition, persons with a registration type of Investigator (IVR), Non-Physician Investigator (NPIVR), or Associate Plus (AP) must complete their annual registration using CTEP’s web-based Registration and Credential Repository (RCR) at <https://ctepcore.nci.nih.gov/rcr>.

RCR utilizes five-person registration types.

- IVR — MD, DO, or international equivalent.
- NPIVR — advanced practice providers (e.g., NP or PA) or graduate level researchers (e.g., PhD);
- AP — clinical site staff (e.g., RN or CRA) with data entry access to CTSU applications such as the Roster Update Management System (RUMS), OPEN, Rave, acting as a primary site contact, or with consenting privileges.
- Associate (A) — other clinical site staff involved in the conduct of NCI-sponsored trials; and
- Associate Basic (AB) — individuals (e.g., pharmaceutical company employees) with limited access to NCI-supported systems.

RCR requires the following registration documents:

Documentation Required	IVR	NPIVR	AP	A	AB
FDA Form 1572	✓	✓			
Financial Disclosure Form	✓	✓	✓		
NCI Biosketch (education, training, employment, license, and certification)	✓	✓	✓		
GCP training	✓	✓	✓		
Agent Shipment Form (if applicable)	✓				
CV (optional)	✓	✓	✓		

An active CTEP-IAM user account and appropriate RCR registration is required to access all CTEP and Cancer Trials Support Unit (CTSU) websites and applications. In addition, IVRs and NPIVRs must list all clinical practice sites and Institutional Review Boards (IRBs) covering their practice sites on the FDA Form 1572 in RCR to allow the following:

- Addition to a site roster
- Assign the treating, credit, consenting, or drug shipment (IVR only) tasks in OPEN
- Act as the site-protocol Principle (PI) on the IRB approval; and
- Assign the Clinical Investigator (CI) role on the Delegation of Tasks Log (DTL).

In addition, all investigators acting as the Site-Protocol PI (investigator listed on the IRB approval), consenting/treating/drug shipment investigator in OPEN, or as the CI on the DTL must be rostered at the enrolling site with a participating organization.

Additional information is located on the CTEP website at <https://ctep.cancer.gov/investigatorResources/default.htm>. For questions, please contact the RCR **Help Desk** by email at [contact].

13.4 CTSU Registration Procedures

Permission to view and download this protocol and its supporting documents is restricted and is based on person and site roster assignment housed in the CTSU Regulatory Support System (RSS).

This study is supported by the NCI Cancer Trials Support Unit (CTSU).

a. **IRB Approval:**

For CTEP and Division of Cancer Prevention (DCP) studies open to the National Clinical Trials Network (NCTN) and NCI Community Oncology Research Program (NCORP) Research Bases after March 1, 2019, all U.S.-based sites must be members of the NCI Central Institutional Review Board (NCI CIRB). In addition, U.S.-based sites must accept the NCI CIRB review to activate new studies at the site after March 1, 2019. Local IRB review will continue to be accepted for studies that are not reviewed by the CIRB, or if the study was previously open at the site under the local IRB. International sites should continue to submit Research Ethics Board (REB) approval to the CTSU Regulatory Office following country-specific regulations.

Sites participating with the NCI CIRB must submit the Study Specific Worksheet for Local Context (SSW) to the CIRB using IRBManager to indicate their intent to open the study locally. In order for the SSW approval to be processed, the Signatory Institution must inform the CTSU which CIRB-approved institutions aligned with the Signatory Institution are participating in the study. The NCI CIRB's approval of the SSW is automatically communicated to the CTSU Regulatory Office, but sites are required to contact the CTSU Regulatory Office at [contact] to establish site preferences for applying NCI CIRB approvals across their Signatory Network. Site preferences can be set at the network or protocol level. Questions about establishing site preferences can be addressed to the CTSU Regulatory Office by email or calling [name].

Sites using their local IRB or REB, must submit their approval to the CTSU Regulatory Office using the Regulatory Submission Portal located in the Regulatory section of the CTSU website. Acceptable documentation of local IRB/REB approval includes:

- Local IRB documentation.
- IRB-signed CTSU IRB Certification Form; and/or
- Protocol of Human Subjects Assurance Identification/IRB Certification/Declaration of Exemption Form.

In addition, the Site-Protocol Principal Investigator (PI) (i.e. the investigator on the IRB/REB approval) must meet the following criteria in order for the processing of the IRB/REB approval record to be completed:

- Holds an active CTEP status;
- Rostered at the site on the IRB/REB approval (*applies to US and Canadian sites only*) and on at least one participating roster;

- If using NCI CIRB, rostered on the NCI CIRB Signatory record;
- Includes the IRB number of the IRB providing approval in the Form FDA 1572 in the RCR profile; and
- Holds the appropriate CTEP registration type for the protocol.

Additional Requirements

Assignment of site registration status in the CTSU Regulatory Support System (RSS) uses extensive data to make a determination of whether a site has fulfilled all regulatory criteria including but not limited to the following:

- An active Federal Wide Assurance (FWA) number;
- An active roster affiliation with the Lead Protocol Organization (LPO) or a Participating Organization (PO); and
- Compliance with all protocol-specific requirements (PSRs).

b. **Downloading Site Registration Documents:**

Download the site registration forms from the protocol-specific page located on the CTSU members' website. Permission to view and download this protocol and its supporting documents is restricted based on person and site roster assignment. To participate, the institution and its associated investigators and staff must be associated with the LPO or a Protocol Organization (PO) on the protocol. One way to search for a protocol is listed below.

- Log in to the CTSU members' website (<https://www.ctsu.org>) using your CTEP-IAM username and password;
- Click on *Protocols* in the upper left of the screen
 - Enter the protocol number in the search field at the top of the protocol tree; or
 - Click on the By Lead Organization folder to expand, then select *[Corresponding Organization]*, and protocol number **S1801**.
- Click on *Documents*, select *Site Registration*, and download and complete the forms provided. (Note: For sites under the CIRB, IRB data will load automatically to the CTSU.)

c. **Submitting Regulatory Documents:**

Submit required forms and documents to the CTSU Regulatory Office using the Regulatory Submission Portal on the CTSU website.

To access the Regulatory Submission Portal log in to the CTSU members' website, go to the Regulatory section and select Regulatory Submission.

Institutions with participants waiting that are unable to use the Regulatory Submission Portal should alert the CTSU Regulatory Office immediately at [name] in order to receive further instruction and support.

d. **Checking Your Site's Registration Status:**

Site registration status may be verified on the CTSU members' website.

- Click on *Regulatory* at the top of the screen;
- Click on *Site Registration*; and
- Enter the sites 5-character CTEP Institution Code and click on Go.
 - Additional filters are available to sort by Protocol, Registration Status, Protocol Status, and/or IRB Type.

Note: The status shown only reflects institutional compliance with site registration requirements as outlined within the protocol. It does not reflect compliance with protocol requirements for individuals participating on the protocol or the enrolling

investigator's status with NCI or their affiliated networks.

